A RANDOMIZED TRIAL OF PROJECT IMPACT, AN EVIDENCE-BASED INTERVENTION FOR INFANTS AND TODDLERS WITH AUTISM SPECTRUM DISORDER

Principal Investigator: [name]

Version 6: 3/1/2021

IRB Protocol #842506; NCT04729127

A Randomized Trial of Project ImPACT, an evidence-based intervention for infants and toddlers with autism spectrum disorder RESEARCH PROTOCOL

ABSTRACT

One in 59 children has ASD; approximately 40% are diagnosed before three years of age. ² The Individuals with Disabilities Education Act (IDEA)¹⁷ entitles these children to services that address their delays and prepare them for school. Evidence-based treatments for infants and toddlers with ASD include a therapist-implemented component and parent training, with the expectation that parents will continue the intervention between therapist visits. There is growing interest in the effects of parent-mediated intervention for young children with ASD, 18 driven by the belief that empowering parents to use intervention strategies within daily routines is more developmentally appropriate than intensive, therapist-led interventions. 11 High-quality, parentmediated EI improves long-term outcomes for children with ASD across a range of developmental domains. 7,16,19 It also improves parental self-efficacy and treatment engagement. 7,20,21 Several efficacious parent-mediated interventions have been developed in research settings. Beyond the question of efficacy - the extent to which these interventions achieve outcomes under ideal circumstances – there has been a growing call to test their effectiveness – the extent to which they work under real-world circumstances.^{9,10} Researchers have pointed to the 'voltage drop' that occurs when evidence-based interventions move from the lab to the community, ²² and the need to test whether they are successful when community clinicians use them.²³⁻²⁵ The World Health Organization bemoans the lack of effectiveness trials, which inhibits its ability to strongly recommend parent training. ²⁶ While Project ImPACT is designed for community implementation, it has not been subject to a rigorous effectiveness trial.

Services in publicly-funded EI often are limited to 1-to-3 hours a week of therapist contact. Little data are available on how many contact hours are necessary to change parent behavior, produce positive child outcomes, or the associated cost-benefit. One small, non-randomized study found that a low dose of Project ImPACT was enough to improve parent-reported outcomes relative to the comparison group, but the sample size, lack of randomization, use of highly-trained academic clinicians, and lack of a comparison group at another dose of Project ImPACT limits interpretation of these findings. ¹⁹ In addition to providing data on effectiveness, our study also will estimate cost-effectiveness. There is little evidence about cost-effectiveness, which is needed to support resource allocation decisions.²⁷ While several studies simulate data to suggest that the costs of early intervention are offset by long-term savings, ²⁸⁻³¹ only two studies comprise a formal, rigorous cost-effectiveness evaluation. 32,33 None has examined the relative benefit of an intervention at different doses, a critically important question to our community partners. In Philadelphia, the infant and toddler early intervention program spends \$10 million annually for services for children with ASD. In the US, these services typically are funded with public dollars. It is incumbent upon service systems to support interventions that produce meaningful outcomes and to avoid the use of public funding for interventions below or above an effective dose. With better information about effective dose of intervention, service systems can more effectively direct and allocate public dollars.

Our pilot study will address a number of pressing questions, including: Can community clinicians successfully coach parents of children with ASD in evidence-based practice to achieve positive outcomes for their children and themselves? What dose is necessary to achieve change?

And what is the cost effectiveness of implementing evidence-based interventions at different doses? This project has the potential to dramatically improve the services families of young children with ASD in Philadelphia receive, and significantly improve long-term outcomes. Successful completion of the proposed study would provide the EI system with the information needed to bring this type of intervention to scale across the entire system. Findings from this pilot trial would serve as the foundation for an application for federal funds to conduct a large-scale, system-wide study of Project ImPACT implemented in all Philadelphia agencies serving infants and toddlers with ASD.

RESEARCH PLAN

The proposed study is highly innovative. Foremost, the choice of intervention, the study questions and the study design all were developed in partnership with leaders from Philadelphia's infant and toddler early intervention system, which increases the ecological validity and utility of the findings, and the potential for the study to lead to lasting changes in Philadelphia's early intervention system. Second, the study comprises a field trial of an intervention for young children with ASD using community (as opposed to university-based) clinicians to train parents in the intervention. This model of testing effectiveness is rare, with similar studies published mostly from data collected outside of the United States. Third, our sample will be culturally and socioeconomically diverse, a limitation of almost all prior autism intervention studies. Fourth, we propose to test two doses of the same intervention. While determining the most effective dose of intervention is of critical importance to the field, there has been no head-to-head comparison in a randomized trial. Fifth, we propose to measure family as well as child outcomes, which rarely have been reported in intervention trials.

Setting for all Research Activities

In Philadelphia, children ≤36 months of age with ASD are eligible for treatment through the infant and toddler early intervention program. Risk is determined using the Modified Checklist for Autism in Toddlers. Thirteen agencies provide these services. They use an interdisciplinary treatment approach, have a treatment philosophy that supports parent-mediated intervention, and provide home-based services. The early intervention system projects that >800 children with autism ≤36 months of age will receive services next year. On average, children receive 3.4 hours/week of services, about one hour of which comprises "specialized instruction," which Project ImPACT will replace. Children will retain all other services. In specialized instruction, therapists: 1) design learning environments and activities that promote skill acquisition; 2) plan activities that address the outcomes on the individualized family service plan; 3) provide families with information, skills and support to enhance child skill development; and 4) work with the child and family to enhance the child's development. Specialized instructors typically are bachelors-prepared individuals with early child development training.

Aim 1: Compare outcomes in young children (social communication and development) and their parents (stress and self-efficacy) randomized to one of three groups: A) treatment as usual, B) Project ImPACT delivered at 1 hour/week and C) Project ImPACT delivered at 4 hours/week.

Overview

We will compare the outcomes of young children and their parents randomized to three groups: A) treatment as usual, B) 6 months of Project ImPACT at 1 hour/week and C) 6 months of Project ImPACT at 4 hours/week. Observations of regular early intervention sessions between families and clinicians will provide evidence of adherence to the Project ImPACT intervention. Observations of parent and child interactions as well as direct assessments with enrolled children over the course of 6 months, will give information on changes in social communication and parent responsiveness and self-efficacy.

Sample

Clinicians. We will recruit 3 clinicians from each of the 6 participating agencies (18 total). Agencies employ an average of 43 clinicians (range 21-64). Clinicians employed in these agencies have a Bachelor's or Master's degree in a related field, such as psychology, education, or speech pathology. Inclusion criteria are that the clinician: 1) has ≥ 5 children with ASD on their caseload; 2) agrees to participate in training and consultation if selected for one of the Project ImPACT arms; 3) identifies and obtains consent-to-contact forms for families on his or her caseload; and 4) completes the clinician study measures.

Children and their families. We will recruit 3 children per clinician (totaling 54 children, 54 parents). Inclusion criteria are that children: 1) be < 30 months of age (so that they can receive ≥ 6 months of intervention; 2) have a classification of autism or high autism risk as determined by the EI system; 3) be receiving early intervention services through the infant and toddler program and be participating in telehealth sessions if applicable; and 4) have a parent willing to complete the parent measures that are part of this study.

Setting

Assessments and fidelity observations will occur in the family's home, the usual provision of family-based early intervention services. The 2 day ImPACT training workshop will take place at a mutually desired upon location in Philadelphia convenient for clinicians to attend. Ongoing supervision and consultation will take place on video conferencing and phone calls.

Changes in response to COVID-19: The early intervention system is providing all direct service to families via tele-intervention. The research team will not visit families' home for any research activities until local and state authorities indicate that in-home intervention can be resumed. All research activities will be conducted remotely via tele-intervention, shared video recordings, and electronic surveys. Consistent with all services being delivered by the early intervention system, Project ImPACT and treatment as usual will be delivered via tele-intervention. The research team will join tele-intervention sessions for fidelity monitoring and coaching. Direct observation assessments will now be conducted via observations of self-recorded parent-child play interactions. Per these changes, families should have the ability and technology to participate in tele-health sessions with their EI provider in order to participate in the study.

Measures

Child Outcomes (all measures collected at baseline and 6 months):

Changes in Social Communication will be measured using the communication and social domains of the *Vineland Adaptive Behavior Scales–3rd Edition*⁴³ and the *Preschool Language Scales–5th Edition* (PLS). The Vineland is a standardized parent report survey of adaptive functioning that has been normed on individuals ages birth to 90 years. It has excellent psychometric properties

and has been used in many studies of children with autism. Previous research has shown that Communication and Social Domain standard scores are sensitive to change in response to ImPACT. 19,44 The PLS is an interactive direct assessment of developmental language skills that can be given to children birth to seven years. Primary domains include auditory comprehension and expressive communication. It is designed to test a full range of communication skills across the developmental spectrum (including attention, play, gesture, and social communication). It has demonstrated strong reliability and validity across a diverse population, including clinical samples and children with ASD. We will use standard scores on auditory comprehension and expressive communication, as well as total standard scores, in the analyses. A research team member trained to reliability of administration will administer the PLS under the supervision of a licensed psychologist.

Changes in response to COVID-19: The Vineland will be administered to parents via a secure electronic survey link, instead of in person.

Children's Social Communication will be measured using the *Brief Observation of Social Communication Change (BOSCC)* scoring applied to the parent-child interaction videos, instead of the Preschool Language Scales. The BOSCC is an observational coding scheme designed to be sensitive to changes in social communication behavior, easily used by naïve, minimally trained examiners and coded relatively quickly. The BOSCC has strong interrater and test-retest reliability, sensitivity to change, and evidence of convergent and discriminative validity. The BOSCC scoring procedure will be used to measure child social communication behaviors during a parent-child play interaction. The BOSCC does not require direct contact with the parent or child to administer, so is an appropriate outcome measure to use in response to the COVID-19 pandemic. Parents will self- record a 10-minute play interaction between the parent and child using their phone, tablet, or any personal device and will share the recording with the research team via a secure Penn Medicine ShareFile link. ShareFile is a Citrix program that allows its users to share and receive large files securely.

Parent Outcomes (All measures will be completed at baseline, 3 months, and 6 months)

Parenting Self-Efficacy will be measured using the Early Intervention Parenting Self-Efficacy Scale (EIPSES), ⁴⁵ a 16-item self-report measure that examines parents' beliefs about their ability to produce positive changes and promote optimal development in their child with a disability. It measures two dimensions of self-efficacy: Parent Outcome Expectations and Parent Competence. Parents rate items from 1 ("Strongly disagree") to 7 ("Strongly agree") with higher scores indicative of higher parenting self-efficacy. The EIPSES has strong psychometric properties and been used in a number of studies of families receiving Part C services.

Parent Quality of Life will be measured using the World Health Organization WOL Assessment-Brief (WHOQOL-BREF), a short version of the WHOQOL-100 scales. The 26-item questionnaire covers the four dimensions of QOL (physical, psychological, environmental, and social domains). The instrument measures the degree to which the respondent subjectively evaluates their satisfaction with different aspects of their life from a score ranging between 1 (very dissatisfied/very poor) and 5 (very satisfied/very good).

Changes in response to COVID-19: The EIPSES and WHOQOL-BREF will be administered electronically via a link unique to each participant sent via RedCap.

Parent Responsiveness will be measured using the Parenting Interactions with Children: Checklist of Observations Linked to Outcomes (PICCOLO), ⁴⁶ a checklist of 29 observable, developmentally supportive parenting behaviors with children ages 10-47 months. The PICCOLO has four domains: Affection, Responsiveness, Encouragement, and Teaching. It is a strengths-based measure of parenting interactions that predicts children's early social, cognitive, and language development with solid psychometrics. A brief (10 minute) parent-child interaction will be video recorded (see below) at each time point; members of the research team blind to study arm or time point will score the checklist. Total scores on each domain are used to monitor change in parenting behaviors.

Parent Treatment Adherence will be assessed through a videotaped parent-child interaction at home. Parents will be asked to: 1) interact with their child for 10 minutes in the way they typically would during play; and 2) have a snack or meal with their child. Parent behavior will be scored for use of the intervention strategies using the Project ImPACT Intervention Fidelity Checklist. Each of 6 strategies is scored on a scale of 1 ("Parent does not implement throughout session") to 5 ("Parent implements throughout session), and then averaged to form an overall fidelity rating for each routine. Ratings for the play and snack routines will be averaged to form an overall fidelity rating. Several studies have used the Project ImPACT fidelity checklist, which shows strong interrater reliability. ^{19,20,44} Trained observers blind to group assignment and time point will score it.

COVID-19 Changes: Parents will self-record a 10-minute play interaction and a snack routine with their child using their phone, tablet, or other personal device., instead of having a research team member record the session during a home visit. The same 10-minute play interaction will be used to code for changes in children's social communication as described above for the BOSCC, changes in parent responsiveness for the PICCOLO, and changes in parent treatment adherence (using the Project ImPACT Intervention Fidelity Checklist) for each time point. Parents will share the video with the research team using a secure Sharefile link.

Other Important Covariates will include 1) parents' socio-demographic characteristics. Parents will complete a form that includes demographics, family composition, education and financial resources using the relevant US Census Survey questions; and 2) clinician training and experience, which will be measured through a brief questionnaire that asks questions regarding degree, years in the field, experience with children with autism and experience with Project ImPACT components.

COVID-19 changes: The socio-demographic survey will be administered to parents via a unique secure electronic Redcap survey link.

Procedure

Clinician training

[name] and the MSU research team will train community clinicians assigned to the Project ImPACT groups using a modified version of the published provider preparation protocol.⁴⁰ This 25-hour training will consist of a 6-hour, self-paced online tutorial, followed by a 2-day interactive workshop that covers the program's rationale and critical elements of the intervention techniques.

COVID-19 changes: The interactive workshop will be delivered to clinicians remotely via Zoom instead of in-person. The workshop will be delivered over 4 days, in 3.5 hour sessions, instead of 2 full days to accommodate the remote learning experience.

Following introductory training, clinicians in each agency will participate in bi-weekly group consultation meetings with Penn consultants (see below) via videoconferencing. During these 1-hour group meetings, clinicians will present their Project ImPACT cases to the other clinicians in their agency and receive feedback and problem solving from the Penn consultant. Each clinician also will receive a monthly consultation visit in the field. During these 1-hour sessions, the consultant will observe an intervention session, complete the coaching fidelity form, and provide feedback to the clinician on Project ImPACT implementation. [name] team has successfully used this remote consultation model to train clinicians to fidelity in Project ImPACT with high ratings of satisfaction, self-efficacy, and attendance from clinicians who participated in the training.⁴¹

To prepare Penn staff to consult in the field, [name] and the MSU research team will train them to fidelity in Project ImPACT and its coaching model, and fidelity monitoring. This training will include the same introductory training described above, consultation meetings with MSU study staff to provide feedback on program implementation with a family with ASD via videoconferencing; and obtaining reliability on parent treatment adherence and coaching fidelity scoring for master session tapes. Once Penn staff have been trained to fidelity in coaching and reliability in fidelity monitoring, they will meet biweekly with MSU staff via video-conferencing for supervision as they provide monthly consultation sessions to community clinicians using Project ImPACT. MSU research staff also will conduct twice-a-month cross-site video-based fidelity checks to ensure that Penn staff is providing training and feedback to the clinicians implementing the program in a way that is consistent with the Project ImPACT model.

Clinician Fidelity will be measured using the Project ImPACT Coaching Fidelity Checklist.¹ Clinicians assigned to the two active treatment groups will self-monitor their coaching fidelity as part of the implementation procedure. We also will observe clinicians monthly to ensure accurate self-monitoring in the active treatment groups and to capture the extent to which clinicians in the treatment as usual group use any elements of ImPACT. Previous research indicates high interrater reliability between self and observer ratings on the coaching fidelity form (99% exact agreement);⁴² thus we anticipate that self-ratings will provide an accurate measure of clinician behavior.

Cluster Randomized Study Design

Six agencies will be blocked into groups of 3 based on agency size and location. Within each group of three, each agency will be randomized to one of three conditions: 1) treatment as usual; 2) ImPACT at a dose of 1 hour/week over 6 months; and 3) ImPACT at 4 hours/week over 6 months.

Statistical Analysis for Aim 1

Outcomes will be analyzed as continuous variables at the child or parent level across time. Initially all outcomes will be described using summary statistics (means, medians, and estimates of variance). The longitudinal nested random effects linear models will be used for each outcome; the models will consist of three levels of random effects to adjust for individual child/parent, agency and clinician variability. For each measure, the analysis dataset will contain one observation with each subject's outcome measure at baseline and follow-up. The dependent variable in each model will be the measure of outcome at each time point. The independent variables will include a categorical variable for time period (baseline, 3 months, or 6 months), group (ImPACT_1hr/wk, ImPACT_4hr/wk or comparison), and their interaction. The magnitude and statistical significance of the beta coefficient for the interaction will provide an intent-to-treat assessment of the extent to which the intervention group improved relative to the comparison

group. Because agencies are randomly assigned, we expect clinicians and children in our intervention and comparison groups to be similar across baseline characteristics; however, if we find between-group differences we will control for them in our regression models.

Aim 2: Examine the cost effectiveness of Project ImPACT at different doses.

Overview

The purpose of the cost evaluation is to determine both the cost of implementing Project ImPACT in Philadelphia, and the cost associated with any additional benefit of one treatment arm over the other. Both questions are of great interest to our community partners and system administrators in general. Our cost-effectiveness analysis will take two perspectives: 1) a service perspective, which is of particular interest to policy makers and includes hospital, community and school-based health, social and education services; and 2) a societal perspective to capture the full economic implications, which also include parental out-of-pocket costs (insurance copayments, unreimbursed therapies and materials etc.), child care and schooling costs, productivity losses (time off work due to child's condition), and unpaid care.

Measures

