
capital approach, which involves multiplying time off work by the parent's wage rate.⁵⁰ We will calculate informal care costs using the market price approach that applies the price that would be paid if the care were provided by a formal care giver.⁵¹ Finally, we will calculate total costs for each agency and then averaged across centers within each study arm to determine average costs per study condition.

Data Analysis

The outcomes of different study arms will be combined with their respective costs to provide a measure of relative cost-effectiveness that can be compared to other interventions employing the same measure of outcome. The effects will be improvements in child and parent outcomes. Using the estimated mean cost and mean effect per patient by intervention group, we will construct an incremental cost-effectiveness ratio for each outcome for which Project ImPACT shows a significant effect. Incremental cost-effectiveness will be computed as the ratio of the difference in mean costs (incremental cost) to the difference in mean effects (incremental effect), and will represent the additional cost per additional improvement in child development and social communication scores and parent stress and self-efficacy scores, of one intervention arm compared to another. A joint distribution of incremental mean costs and effects for the intervention arms being compared will be generated using non-parametric bootstrapping.⁵² We will use these data to explore the probability that each treatment is optimal choice, subject to a range of possible maximum values (ceiling ratio) that a decision maker might be willing to pay for an additional improvement in child or parent outcome score. Cost-effectiveness acceptability curves (CEAC) will be generated by plotting these probabilities for a range of possible values of ceiling ratios. 53,54 CEACs are a standard decision-making approach to dealing with the uncertainty around the estimates of expected costs and effects and uncertainty regarding the maximum CER a decision maker would consider acceptable.⁵⁴ We will examine baseline characteristics across intervention groups to determine whether randomization was successful in balancing observed baseline covariates. If there is unbalanced allocation in baseline characteristics, we will use net-benefit regression to estimate directly in a regression framework.

Statistical Power

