We base our statistical power analysis upon Aim 1, our primary aim, which tests the effects of Project ImPACT on child and parent outcomes. Prior studies of Project ImPACT and related parent-mediated interventions indi-cate a large effect on parent treatment adherence (.90-1.30), and a moderate effect on child outcomes (.34-.70).16,19,42 Meta-analytic reviews of studies of parent-implemented interventions for children with ASD report effects of .8 to 1.1.26 We used Power and Precision software, and assumed an alpha of 0.05, and that all tests are 2-tailed. We will have enrolled 3 clinicians in each agency and 3 children per clinician (18 subjects per intervention group). Due to statistical software limitations in addressing multiple levels of clustering in power estima-tion, we adopted two perspectives. First, we explored potential effect sizes (Cohen's d) with nesting of clinicians within agencies. Second, we estimated potential effect sizes with nesting of patients within clinicians. We as-sume an intra-class correlation of 0.05. In the first case, we calculate that we will have power of 80% to detect a moderate intervention effect of d=0.66. In the second case, we calculate that we will have power of 80% to de-tect a moderate intervention effect of d=0.53.

PROTECTION OF HUMAN SUBJECTS

Research will not begin until the Institutional Review Boards of the University of Pennsylvania and the City of Philadelphia approve the proposed study.

Characteristics of Population

We anticipate the sample of parent-child dyads will be 45% African American, 26% Latino, 18% Caucasian, 6% Asian, 2% American Indian/Native American, and 3% multi-racial. Children will be less than 3 years of age, and will either have a diagnosis of autism spectrum disorder or be identified as at-risk for autism by the early intervention system, as children under three years of age do not need a formal diagnosis to receive autism-specific treatment. We anticipate that 75% of the children will be male based on the sex distribution of autism. Participants will be excluded if they do not speak English. This is due to the procedures of the project, which include coding of videos of early intervention sessions. The team currently does not have capacity to code videos that are not in English. Participants will not be excluded based on their gender or past experience.

Data to be collected from Human Subjects

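### Aim 1 has no primary outcome and no multiplicity control, and significance then decides which outcomes get a cost-effectiveness ratio in Aim 2

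*Combined protocol and SAP*

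**What the plan says.** The Statistical Power section reads: "We base our statistical power analysis upon Aim 1, our primary aim, which tests the effects of Project ImPACT on child and parent outcomes". It names no single outcome or time point as primary, and neither does any other section. The same section "assumed an alpha of 0.05, and that all tests are 2-tailed". That is the only significance level in the document.

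Under Statistical Analysis for Aim 1, "The longitudinal nested random effects linear models will be used for each outcome". The model contains time, "group (ImPACT_1hr/wk, ImPACT_4hr/wk or comparison), and their interaction". The intention-to-treat result is read from this: "The magnitude and statistical significance of the beta coefficient for the interaction". There is no hierarchy, adjustment or family-wise error rate.

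The Data Analysis section of Aim 2 adds a rule that depends on those tests: "we will construct an incremental cost-effectiveness ratio for each outcome for which Project ImPACT shows a significant effect".

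The Measures section lists the outcomes. Child outcomes, at baseline and 6 months, are the Vineland, "using the communication and social domains of the" instrument, and the BOSCC, "scoring applied to the parent-child interaction videos, instead of the Preschool Language Scales". Parent outcomes, at baseline, 3 and 6 months, are EIPSES (two dimensions), WHOQOL-BREF (four domains), PICCOLO (four domain totals) and treatment adherence (one overall rating).

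**The concern.** A reader cannot work out which result answers the question of whether Project ImPACT works. The Aim 1 statement names child social communication and development, and parent stress and self-efficacy. The Measures section has no stress instrument but adds quality of life, responsiveness and adherence. The outcome set is therefore not settled, and nothing ranks its members.

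Two things are at stake. First, with many tests and no rule, at least one nominally significant interaction is likely even if neither dose does anything. Second, the Aim 2 rule carries this forward. An outcome enters the cost-effectiveness analysis because its test was significant, and estimates selected that way tend to be too large. A denominator that is too large makes the cost per unit of improvement look too low. The protocol intends these results to guide the use of public funds and a system-wide scale-up.

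**Working it through.** **The plan's own figure.** The plan states neither a number of tests nor a family-wise error rate, so there is nothing to reproduce on this point. Its detectable effects (d = 0.66 and 0.53) are used below only to scale the cost of the fix. They do not reproduce from 18 per group: (1.96 + 0.84) × √(2/18) = 0.93 before any clustering. That is a separate issue.

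**Scores.** Vineland 2, BOSCC 1, EIPSES 2, WHOQOL-BREF 4, PICCOLO 4, adherence 1: 14 in all, 3 child and 11 parent. Domain scoring is stated for the Vineland and PICCOLO. For EIPSES and WHOQOL-BREF, separate analysis of each dimension is an assumption.

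**Tests, each dose against usual care.**
- All domains, 6 months only: 14 × 2 = 28.
- All domains, both parent follow-ups: 3 × 2 + 11 × 2 × 2 = 50.
- One total each for EIPSES, WHOQOL-BREF and PICCOLO leaves 7 scores (3 child, 4 parent): 7 × 2 = 14 at 6 months, and 3 × 2 + 4 × 2 × 2 = 22 with both parent follow-ups.
- PICCOLO by domain, one total each for EIPSES and WHOQOL-BREF leaves 10 scores: 10 × 2 = 20 at 6 months.

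The 1-hour against 4-hour contrast is not counted.

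**Independent tests, no true effects.** The chance of any false significant result is 1 − 0.95^k. In the benefit direction each two-sided test contributes 0.025, so the chance is 1 − 0.975^k.

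| Tests k | Either direction | Benefit direction |
|---|---|---|
| 14 | 0.51 | 0.30 |
| 20 | 0.64 | 0.40 |
| 22 | 0.68 | 0.43 |
| 28 | 0.76 | 0.51 |
| 50 | 0.92 | 0.72 |

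**Correlated tests.** The documents give no correlations, so these are assumed. Multivariate normal simulation, 200,000 draws, with correlation 0.5 between the two dose contrasts because they share the usual-care arm. The first column gives the correlation within instrument / between instruments / over time.

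| Setting | 28: either | 28: benefit | 50: either | 50: benefit |
|---|---|---|---|---|
| 0 / 0 / 0 (shared arm only) | 0.73 | 0.48 | 0.91 | 0.69 |
| 0.5 / 0.2 / 0.6 | 0.66 | 0.37 | 0.83 | 0.51 |
| 0.7 / 0.5 / 0.7 | 0.52 | 0.26 | 0.68 | 0.37 |
| 0.8 / 0.6 / 0.8 | 0.45 | 0.23 | 0.58 | 0.30 |

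The two middle rows give the quoted ranges of 52% to 83% and 26% to 51%. The last row is a very high correlation, shown as a limit.

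**Size of the selection effect.** With 18 per arm, no clustering and a change-score SD equal to the outcome SD (both assumptions), two-sided significance needs an observed difference of about 2.03 × √(2/18) = 0.68 SD. The protocol expects child effects of .34 to .70. An outcome that passes the Aim 2 gate would then show an effect near or above the top of that range, whatever the true effect.

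**Cost of splitting alpha.** The detectable effect is proportional to z(1 − α/2) + z(0.80). For the first Holm step with two contrasts (α = 0.025): (2.241 + 0.842) / (1.960 + 0.842) = 1.10. Taking the plan's figures as given, 0.53 becomes 0.58 and 0.66 becomes 0.73. With three contrasts (α = 0.0167): (2.394 + 0.842) / 2.802 = 1.15.

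**The case against.** Several counter-arguments are sound and limit the claim.

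- **Pilot status.** The protocol calls this a pilot and plans a larger study. How strict family-wise control should be with 54 children is partly judgement. But the plan also claims 80% power, judges effect by significance and makes significance the gate to Aim 2, so the label does not answer the point.
- **Direction of error.** A reader might infer that a false claim of benefit is more likely than not. The documents do not support this. Tests are two-tailed. At 28 tests the benefit-direction risk is 0.51 only under full independence, and 0.48 once the shared usual-care arm is allowed for. At 50 tests it depends on unknown correlations.
- **Count.** 28 to 50 is a reading of the Measures section, not a statement in the plan; 14 to 22 is also tenable.
- **Ratios per test.** A reader might infer that every significant test produces a ratio. The rule works per outcome, so at most 14 on the full count. The same section also describes the ratios with a shorter list: child development, social communication, parent stress and self-efficacy.
- **Wording and uncertainty.** The Aim 1 text cites magnitude as well as significance, and Aim 2 uses bootstrapping and acceptability curves. These show uncertainty within a selected outcome but do not undo the selection.
- **Choice of primary.** No outcome is the obvious one. The BOSCC is scored from play that the parent records and joins, and blinded coding is stated for PICCOLO and adherence but not for the BOSCC. The protocol describes the Vineland domains as sensitive to change with ImPACT.

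**Conclusion.** The point holds in this form: there is no primary outcome or time point, no multiplicity control, and a rule that lets significance choose the Aim 2 outcomes. The last part makes it more than missing detail, because following the plan as written produces the selection.

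The risk of at least one false significant result is 76% to 92% for 28 to 50 independent tests, 51% to 68% for 14 to 22, and about 52% to 83% for 28 to 50 tests under the two correlation settings. On the benefit side alone the figures are 51% to 72%, 30% to 43%, and 26% to 51%. Even 26% is about ten times the 2.5% of a single test.

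These figures assume no true effect on any outcome, that each test holds its nominal size, that 0.05 from the power section is the level applied, and the stated counts and correlations. The documents do not support a firm claim that a false finding of benefit is more likely than not.

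**What to change.** 1. In the Data Analysis section of Aim 2, drop the significance condition. Compute the ratios and acceptability curves for one or more pre-specified outcomes regardless of p-value.
2. Before any outcome data are seen by arm, designate one primary outcome and time point. The BOSCC at 6 months is one option, provided its coders are stated to be blind to arm and time point, as the plan already states for PICCOLO and adherence. Say how the dose contrasts, including 1 hour against 4 hours, share an overall 0.05. The protocol stresses the head-to-head comparison, so it should not be left out.
3. Report all other scores as secondary or exploratory, with estimates and confidence intervals. State for EIPSES, WHOQOL-BREF and PICCOLO whether totals or domains are analysed.

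The change is to wording and needs no new data. It does have costs. Secondary scores lose confirmatory status. Splitting alpha raises the detectable effect at the first Holm step by about 10% with two contrasts and about 15% with three. In a sample of 18 per arm that loss should be disclosed.
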